Clearing the fog: Is Hydroxychloroquine effective in reducing Corona virus disease 2019 progression: A randomized controlled trial

Registration NO: ID: NCT04491994

Date: 15 May 2020

Study design, setting and participants: This single Centre, parallel open label randomized controlled trial was carried out during 10th April to 31st May 2020 at department of Pulmonology, Pakistan Emirates Military Hospital (PEMH) over 500 patients from both genders between 18-80 years of age. The study design was approved by institutional ethical review committee. The study population was comprised of patients from both genders with Mild confirmed COVID-19 after their written consent. The study protocol and approval documents are available online at ClinicalTrials.gov with trial number of NCT04491994.

Sample size calculation: Sample size was calculated using OPEN EPI with 5% level of Confidence and 80% power to detect a difference and enrolment ration 2:1 between intervention and control group, at a two-sided significance level of $\alpha=0.05$, of 7 days in the median time to clinical improvement between the two groups, assuming that the median time in the SOC group was 14 days and assuming 55% efficacy of HCQ in preventing disease progression and achieving viral clearance at day 7. Calculated sample size was 467, however we used a sample size of 500.

Enrolment procedure: During study period, 672 confirmed PCR positive cases were assessed for eligibility. 132 did not meet selection criteria and subsequently excluded. 540 patients were then enrolled and randomized. Further 20 patients were excluded from analysis as 15 withdrew consent and 5 became symptomatic before first dose of HCQ. During follow up 13 patients were found to be deviated from advised therapy and 7 were lost to follow up yielding a final study population of

500. **Figure 1** summarizes this process. Randomization rules were designed by [name] together with principal investigators and implemented by an independent statistician who was not involved in data analysis. Stratified random sampling was applied to stratify all eligible patients according to age, gender and comorbidities. Computerized random number generator was used and allocation was done in 2:1 sequence. Cards with each group assignment number randomly generated by computer were placed in sequentially numbered envelopes that were opened as the patients were enrolled

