Interventions: A total of 349 patients included in intervention group and 151 in control group. In Hospital, HCQ was given to patients after written consent and after considering its contraindications. Three hundred and forty-nine (349) patients were included in intervention group and given HCQ in addition to standard of care treatment. After 12 hours of randomization HCQ was given. Standard dose of HCQ was 400 mg by mouth twice a day for day one followed by 200 mg 12 hourly for next 5 days. The patients who did not give consent for treatment with HCQ or had a known allergy to HCQ or chloroquine or had another known contraindication to treatment with the study drug, including retinopathy, G6PD deficiency and QT prolongation served as controls. Controls were matched with participants on the basis of age, gender and co morbid and comprised of 151 patients. Standard of care (SOC) treatment comprised of daily oral Vit C (2gms), oral Zinc (50mg), oral Vit-D (alfacalcidol 1ug) and tablet Paracetamol (for body aches/fever), intravenous fluids, hemodynamic monitoring, and laboratory testing for SARS-CoV-2 and baseline blood parameters. Neither patients, nor investigators, nor statisticians were masked to treatment assignment. Lab staff who performed sampling for PCR, basic blood tests and other routine measurement were unaware of treatment information. Data regarding age, co-morbidities, history of contact with a positive patient, days since contact, duration of symptoms, PCR status

with date and base line labs/X-ray chest were recorded. Any patient with day 0 CRP greater than 6mg/dl, Absolute lymphocyte count (ALC) < 1000 or evidence of infiltrates on X-ray chest were excluded. Daily temperature, respiratory rate (RR) and resting O2 saturation with pulse oximetry were monitored in all patients during their hospitalization.

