Operational definitions: A case was considered confirmed on the basis of positivity of RT-PCR of combined Oropharyngeal and Nasopharyngeal swabs. Severity of disease was defined as per criteria designed by WHO¹¹. Mild disease meant Patients with uncomplicated upper respiratory tract viral infection having non-specific symptoms such as low-grade fever (fever < 100F for < 3 days), fatigue, body aches, cough (with or without sputum production), anorexia, muscle pain, sore throat, nasal congestion, anosmia, headache and rarely diarrhea, nausea, and vomiting. PCR sampling was done on day 7 and 14 of admission. Any chronic health condition for which patients were on prior treatment was considered as co morbidity. After start of treatment, development of fever > 101 F for > 72 hours, shortness of breath by minimal exertion (10-Step walk test), derangement of basic lab parameters (ALC < 1000 or raised CRP) or appearance of infiltrates on CXR during course of treatment was labeled as progression irrespective of PCR status. PCR status of patients was checked after 7 days and 14 days of initiation of treatment.

Inclusion and exclusion criteria: Inclusion criteria included (1) Mild Corona virus disease (COVID-19) (2) PCR confirmed infection (3) Hospital admitted patients (4) 18-80 years age Exclusion criteria were (1) Moderate, severe and critical COVID-19 (2) day 0 CRP greater than 6mg/dl, ALC < 1000 or evidence of infiltrates on X-ray chest (3) comorbidity with life expectancy less than 6 months (4) Contraindications to HCQ therapy.

Outcomes: Primary outcome was disease progression within 5 days of start of treatment. This was defined by development of fever > 101 F for > 72 hours, shortness of breath by minimal exertion

(10- Step walk test), derangement of basic lab parameters (ALC < 1000 or raised CRP) or appearance of infiltrates on CXR. Patients underwent 6 hourly axillary temperature check, daily 10 feet walk test, daily Blood counts, CRP and X-Rays on day 0, 3 and 5.

Secondary outcome was Viral clearance. PCR negativity on day 7 and 14 after admission was recorded.

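### The primary 5-day window has no stated time zero common to both arms, and five randomized patients are excluded on a first-HCQ-dose milestone that controls do not have; PCR days 7 and 14 also have two anchors

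*Combined protocol and SAP*

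**What the plan says.** All references are to the combined protocol and SAP.

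- **Primary window.** Outcomes: "Primary outcome was disease progression within 5 days of start of treatment". The components are sustained fever ("development of fever > 101 F for > 72 hours"), breathlessness on a walk test, a low lymphocyte count or raised CRP, or new X-ray infiltrates. Operational definitions gives the same components and labels them progression only once treatment has started.
- **Start of treatment.** Interventions: "After 12 hours of randomization HCQ was given". HCQ patients were "given HCQ in addition to standard of care treatment". Standard of care is listed by content, with no start time. Day 0 is used for entry tests and the X-ray schedule but is not tied to admission, randomization or first dose.
- **Exclusions.** Enrolment procedure: "Further 20 patients were excluded from analysis as 15 withdrew consent and 5 became symptomatic before first dose of HCQ". No corresponding rule is given for controls.
- **PCR timing.** Operational definitions says "PCR sampling was done on day 7 and 14 of admission" and later "PCR status of patients was checked after 7 days and 14 days of initiation of treatment". Outcomes says "PCR negativity on day 7 and 14 after admission was recorded".
- **CRP.** The progression definition gives a number for the lymphocyte count but none for CRP.

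**The concern.** Randomization makes the arms comparable at the moment of randomization. A window that opens at start of treatment keeps that comparability only if the start means the same moment in both arms. Here it is dated for one arm only. The exclusion of five patients shows that the first HCQ dose was used as a gate into the analysis, and controls cannot pass or fail that gate. Early worsening could then be left out of one arm only. The primary outcome covers just five days, so 12 hours is not negligible: 12/120 = 10% of the window.

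The PCR conflict raises the same question for the secondary outcome: from which event are days 7 and 14 counted?

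**Working it through.** **1. Patient flow (Enrolment procedure, Interventions).** 672 − 132 = 540 randomized; 540 − 20 = 520; 520 − 13 − 7 = 500; 349 + 151 = 500. The plan's counts reconcile. The five are part of 15 + 5 + 13 + 7 = 40 post-randomization exclusions.

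**2. Most that the five can change.** Assumption: all five were randomized to HCQ. The arm is not stated; it is inferred from the reference to the first HCQ dose. The restored denominator is 349 + 5 = 354. With x progressors among the 349, the rise in HCQ risk if all five are events is

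(x + 5)/354 − x/349 = (5/354) × (1 − x/349),

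which cannot exceed 5/354 = 1.41 percentage points. The documents give no HCQ risk, so x below is assumed.

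| Assumed x/349 | None of the five an event | All five events | Largest rise (points) | Largest factor on the risk ratio, controls unchanged |
|---|---|---|---|---|
| 17/349 = 4.87% | 17/354 = 4.80% | 22/354 = 6.21% | 1.34 | 1.28 |
| 35/349 = 10.03% | 35/354 = 9.89% | 40/354 = 11.30% | 1.27 | 1.13 |
| 70/349 = 20.06% | 70/354 = 19.77% | 75/354 = 21.19% | 1.13 | 1.06 |
| 105/349 = 30.09% | 105/354 = 29.66% | 110/354 = 31.07% | 0.99 | 1.03 |

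The lower end applies if none of the five met the progression definition; HCQ risk then falls slightly because only the denominator grows.

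**3. Direction under each clock.** Take first dose at exactly 12 h (the text gives no upper limit), a 120 h window, and HCQ-arm events before first dose removed.

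- *One clock from randomization.* HCQ patients can contribute events over hours 12 to 120, which is 108 h; controls over hours 0 to 120, which is 120 h. Early events are missing from one arm only, which favours HCQ.
- *HCQ from first dose, controls from randomization.* HCQ is observed over hours 12 to 132 and controls over hours 0 to 120; both windows last 120 h. With constant hazard λ and no drug effect, risk is 1 − exp(−120λ) in each arm, so there is no bias. A rising hazard works against HCQ and a falling one in its favour.

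The fever component behaves the same way. If more than 72 h of fever must be completed inside the window, onset must fall before hour 120 − 72 = 48 of the clock. Under the second reading that means hours 12 to 60 after randomization for HCQ and 0 to 48 for controls: 48 h each, shifted but not shortened.

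**4. PCR anchors.** Two sentences count days 7 and 14 from admission (one in Operational definitions, one in Outcomes). A third, in Operational definitions, counts from initiation of treatment. They agree only if admission and treatment start fall together. The interval between the two is not given, so the size of the discrepancy cannot be computed.

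**The case against.** The strongest reply is that nothing shows the arms were timed differently. Standard of care went to both arms, and Outcomes gives a single assessment schedule without separating them, so a shared day 0 is plausible. Most components were assessed daily or less often; only temperature was checked every six hours, so a 12-hour offset is near the resolution of the data. This stands: the defect is an unstated time zero. A reader might infer that the arms were in fact misaligned, but the documents do not show that.

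A reader might also infer that a later HCQ clock together with dropped pre-dose cases favours HCQ. It need not, because the two windows are then equally long and the direction depends on the hazard.

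The five are weak evidence of lost events. Their arm is not stated, mild disease as defined already includes symptoms, and progression is defined only after treatment starts. They are also a small part of the 40 exclusions, which need an intention-to-treat answer of their own. All of this stands, and it is why the effect is given as 0 to 5 events. It does not remove the asymmetry: the exclusion milestone exists only for HCQ.

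Finally, Interventions describes controls as patients who refused HCQ or had contraindications, and as matched. That conflicts with the randomization in Enrolment procedure and is the more basic problem. Counting from randomization makes sense only once it is reconciled.

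**Conclusion.** The point holds in limited form. The primary window lacks a stated common time zero, and five randomized patients were excluded on a milestone that controls do not have.

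On a common clock, and assuming all five were HCQ-arm patients, dropping them favours HCQ by at most 1.4 percentage points and possibly by nothing. The relative effect could matter only if progression was uncommon: at an assumed HCQ risk near 5%, the risk ratio could be understated by a factor of up to 1.28. If the HCQ clock ran from first dose, no direction should be claimed. The actual effect on the result cannot be computed from the documents.

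The PCR anchors contradict each other and must be reconciled, but no effect on the result is shown. The missing CRP threshold is a reporting gap. A reader might infer that raised means above the 6 mg/dl entry limit, but no sentence links that limit to the outcome, and a laboratory normal range is an equally possible reading.

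**What to change.** 1. Define time zero as randomization in both arms, and count progression from there to the same 120 h, or the same study day, in both. First reconcile the two accounts of how controls were assigned.
2. Keep the five in their randomized arm and count any progression before first dose. If they have no follow-up data, report the result with none and with all five as events. State how the other 35 post-randomization exclusions (40 − 5) are handled.
3. If the day-5 assessment was timed differently by arm, report its hours from randomization by arm and add a sensitivity analysis limited to events by a common time. If randomization or assessment times were not recorded, say so and state the time zero actually used in each arm.
4. Reconcile the three PCR sentences to one anchor for both arms that matches the actual swab timing.
5. Report the threshold that was used for a raised CRP.

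**Cost.** Revised wording in Outcomes and Operational definitions, and re-derivation of the primary outcome for 500 patients plus the five; no new tests or swabs. The re-derivation depends on times that the documents do not show were recorded. There is one trade-off. If HCQ day-5 tests were timed from first dose, they fall at about 12 + 120 = 132 h after randomization. Counting by study day would then give HCQ up to 12 h more follow-up, while cutting at 120 h would lose those results. The analysis in item 3 makes this visible.
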